4. ANALYSIS POPULATIONS

The purpose of the post-treatment follow-up period is to assess mortality and malignancy, therefore the As-Treated population will be used. The As-Treated population will be defined as described in the Week 52 double-blind treatment period RAP. In addition, four subsets of this overall population will be defined – one for each year of the follow-up period.

As-Treated

The As-Treated population is defined using data from the Week 52 double-blind treatment period. It includes all subjects who were randomized and received at least one dose of study agent. The As-Treated population will group subjects according to the actual treatment administered to the subject based on the treatment that the subject received most of the time (>50% of the time). Therefore, if a subject received an incorrect treatment at more than half the visits, the As-Treated treatment group assignment will differ from the randomized treatment group assignment.

Summary tables which present the number of subjects at Week 52, for use as a denominator for Week 52, will include all subjects in the As-Treated population.

As-Treated Follow-Up Population Subsets

Separate populations will be created to identify which subjects are included in each post-treatment follow-up year (Year 2, Year 3, Year 4 and Year 5). Subjects will be included in the post-treatment follow-up subsets of the As-Treated population and summarized according to the actual treatment administered during the Week 52 double-blind treatment period (as defined for the As-Treated population). It should be noted that subjects in the post-treatment follow-up period will no longer be receiving study treatment.

Subjects will be included in the subset populations based on the completion of the survival status question at the follow-up visits and using nominal visit from the eCRF. The last post-treatment follow-up visit a subject completes will be identified from visits where the survival status question was completed. Completion of the survival status question would include responses of Alive, Dead, Lost to Follow-up or Withdrew Consent. If the response to the survival status question is missing (or the visit is not completed) then this visit will not be included when identifying the last post-treatment follow-up assessment completed.

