Subjects will be included in the population subsets based on the last post-treatment follow-up assessment completed and included in the follow-up subsets for all years up to and including the last post-treatment follow-up visit completed.

Any subject who completes the follow-up assessments as described above will be included in the follow-up subsets, regardless of their status at Week 52.

Population	Definition / Criteria
Year 2 Follow-Up	
 All subjects in the As-Treated population whose last completed post-treatment follow-up visit was Year 2, Year 3, Year 4 or Year 5.
Year 3 Follow-Up	
 All subjects in the As-Treated population whose last completed post-treatment follow-up visit was Year 3, Year 4 or Year 5.
Year 4 Follow-Up	
 All subjects in the As-Treated population whose last completed post-treatment follow-up visit was Year 4 or Year 5.
Year 5 Follow-Up	
 All subjects in the As-Treated population whose last completed post-treatment follow-up visit was Year 5.
Any Year 2 to 5 Follow-Up	
 All subjects in the As-Treated population who completed at least one post-treatment follow-up visit for Year 2 to 5. Note: This will be the same as the Year 2 Follow-Up population. Its main use will be to describe subjects included in data listings.

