6. STUDY POPULATION ANALYSES

6.1. Overview of Planned Study Population Analyses

The study population summaries will be based on the As-Treated population, unless otherwise stated. Summaries will be presented by treatment group and overall.

The number and percentage of subjects at each follow-up visit will be summarized by treatment group and overall. Week 52 will summarize all subjects in the As-Treated population. Summaries of any Year 2 to 5 follow-up, Year 2 follow-up, Year 3 follow-up, Year 4 follow-up and Year 5 follow-up will include subjects in each of the As-Treated population subsets as appropriate.

Important protocol deviations relating to the Years 2 to 5 post-treatment follow-up period will be listed for subjects in the any Year 2 to 5 follow-up subset of the As-Treated population. Protocol deviations will not be assigned to a particular follow-up year, but instead data will be combined across the Years 2 to 5 follow-up period.

For the final Year 5 reporting, demographic and baseline characteristics (including baseline disease activity) will be summarized for subjects in the Year 5 follow-up subset of the As-Treated population. For the interim Year X reporting, demographic and baseline characteristics (including baseline disease activity) will be summarized for subjects in the Year X follow-up subset of the As-Treated population i.e. for Year 2 interim reporting then Year 2 follow-up population subset will be used, for Year 3 interim reporting the Year 3 follow-up population subset will be used, etc.

Descriptive statistics will be used to summarize the continuous demographic and baseline characteristics of age (years) and weight (kg). Counts and percentages of the following categorical demographic and baseline characteristics will be presented: country region/country, gender, Hispanic or Latino origin, age group (≤ 45 years, $> 45 - < 65$ years and ≥ 65 years and then within this last group: $\geq 65 - < 75$ years and ≥ 75 years) and race (Black or Other; see Section 5.2).

The number and percentage of subjects reporting each race and racial combination will be summarized. For subjects who check more than one race category, the race hierarchy rule defined in Section 5.6.2.1 will apply for this summary. Note that this differs to the handling of the race categorization of Black vs Other which ignores the hierarchy rule.

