7.1. All-Cause Mortality

Survival status and mortality will be summarized by nominal follow-up visit.

Survival Status

Survival status by follow-up year will be summarized by treatment group and overall. The number and percentage of subjects will be summarized at each follow-up year for the following categories: alive, deaths (including a breakdown of deaths where COVID-19 was the primary cause of death, per CMQ and Other Deaths for Years 3, 4 and 5 – see Section 5.6.2.4), lost-to-follow-up and withdrew consent. NOTE that the COVID-19 pandemic started after all subjects completed Week 52 and Year 2. Percentages for each follow-up year will be calculated from the number of subjects at the follow-up visit, defined as subjects included in the relevant As-Treated population subset (i.e. Year 2 follow-up, Year 3 follow-up, Year 4 follow-up, Year 5 follow-up).

An additional category ‘Not completed’ will be summarized for follow-up years, this includes subjects who had a subsequent follow-up visit with a non-missing survival status, but did not complete the survival status form at this visit.

For completeness, survival status at the Week 52 visit will also be presented in the same table, with categories of alive, dead, lost to follow-up and unattainable, using subjects in the As-Treated population as the denominator for percentages.

A listing of survival status by follow-up year will be presented, including first commercial Benlysta use.

Deaths by System Organ Class and Preferred Term

A summary of deaths will be produced for each follow-up year separately (Years 2, 3, 4 and 5). For each follow-up year, the summary will include the number and percentage of subjects who died for each SOC, each PT, and overall; based on subjects in the associated year follow-up subset of the As-Treated population and deaths reported during that follow-up year.

By default, the deaths will be sorted by MedDRA SOCs, in descending order from the SOC with the highest total incidence (i.e., summed across all treatment groups) for any deaths within the class, to the SOC with the lowest total incidence. If the total incidence for any two or more SOCs is equal, the events will be presented in alphabetical order. Only SOCs with observed AE PTs will be presented. Repeat sort order for MedDRA PTs within each SOC.

Cumulative Mortality and Follow-up Adjusted Incidence Rate

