7.2. Malignancy

Malignancies will be summarized by nominal follow-up visit for each treatment group and overall.

New Malignancy Percentages

The number and percentage of subjects reporting new malignancies will be summarized at each follow-up year for the categories of: new malignancy, no new malignancy and not completed. Percentages for each follow-up visit will be calculated from the number of subjects at the follow-up visit, defined as subjects included in the relevant As-Treated population subset (i.e. Year 2 follow-up, Year 3 follow-up, Year 4 follow-up, Year 5 follow-up).

The additional category 'Not completed' will be summarized for follow-up years, this includes subjects who had a non-missing survival status at this visit or a subsequent follow-up year, but did not complete the new malignancy form at this visit.

For completeness, new malignancies at the Week 52 visit will also be presented in the same table, using subjects in the As-Treated population as the denominator for percentages.

A listing of new malignancies by follow-up year will be presented, including first commercial Benlysta use.

Malignancies by System Organ Class and Preferred Term

A summary of new malignancies will be produced for each follow-up year separately (Years 2, 3, 4 and 5). For each follow-up year, the summary will include the number and percentage of subjects with new malignancies for each SOC, each PT, and overall; based on subjects in the associated year follow-up subset of the As-Treated population and malignancies reported during that follow-up year.

By default, the malignancies will be sorted by MedDRA SOCs, in descending order from the SOC with the highest total incidence (i.e., summed across all treatment groups) for any malignancies within the class, to the SOC with the lowest total incidence. If the total incidence for any two or more SOCs is equal, the events will be presented in alphabetical order. Only SOCs with observed AE PTs will be presented. Repeat sort order for MedDRA PTs within each SOC.

Cumulative Malignancies and Follow-up Adjusted Subject Incidence Rate

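### In Years 2 to 5 a survival form marked Lost to Follow-up or Withdrew Consent counts as a completed visit, so follow-up counts overstate ascertainment and the yearly SOC/PT percentages include unknown outcomes without showing them

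*SAP*

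**What the plan says.** The relevant plan is the Years 2 to 5 RAP in the SAP. Table numbers are those in its Section 9.4.

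- **What completes a visit (Section 4).** "Completion of the survival status question would include responses of Alive, Dead, Lost to Follow-up or Withdrew Consent". A blank form is treated differently: "If the response to the survival status question is missing (or the visit is not completed) then this visit will not be included" when the last completed visit is identified.
- **Which years the subject enters (Section 4).** Subjects are "included in the follow-up subsets for all years up to and including the last post-treatment follow-up visit completed".
- **Where the subsets are used.** Section 6.1, for Table 1.1: "The number and percentage of subjects at each follow-up visit will be summarized by treatment group and overall". The same section bases the demographic and baseline tables (1.2–1.4) on the subset of the reporting year. Section 7.1, for survival status (Table 3.1): "Percentages for each follow-up year will be calculated from the number of subjects at the follow-up visit". Deaths by SOC/PT (Tables 3.2–3.5) are "based on subjects in the associated year follow-up subset of the As-Treated population and deaths reported during that follow-up year". Section 7.2 words the malignancy tables (3.10–3.13) in the same way: "based on subjects in the associated year follow-up subset of the As-Treated population and malignancies reported during that follow-up year".
- **What is disclosed.** Table 3.1 has rows for alive, deaths, "lost-to-follow-up and withdrew consent", plus a Not completed row for subjects who skipped this form but have a later one. Table 3.9 has a Not completed row for subjects with no malignancy form at that visit. Sections 7.1 and 7.2 describe no such row for the SOC/PT tables. The mock shells are a separate document that I have not seen.
- **Person-time (Sections 5.6.2.6, 5.6.2.8, 5.6.2.9).** Time stops at death, diagnosis, the last-known-alive date or the last contact with a malignancy answer. Subset membership decides which subjects are instead truncated at 365 days.

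**The concern.** A form recording that a subject was lost says nothing about whether that subject died or developed a malignancy. Take a subject alive at Week 52, with no form for Years 2 to 4 and a Year 5 form marked Lost to Follow-up. Section 4 puts that subject in all four yearly subsets. An identical subject whose site left every form blank is in none. Inclusion then depends on form-filling rather than on outcome information.

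Two other parts of the SAP treat the same information differently. Section 11.2.2 of the Week 52 RAP places Lost to Follow-Up under Unknown survival status. Section 5.6.2.8 of the Years 2 to 5 RAP provides for subjects who entered follow-up but have no malignancy answer in Years 2 to 5, and cuts their malignancy time at 365 days. Such a subject can still sit in the denominator of a Year 5 malignancy percentage.

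Table 1.1 is the natural place to look for completeness of the five-year follow-up, and Tables 1.2–1.4 are the only description of who was followed. The outputs are produced each year, including for health authorities (Section 3.1). Section 2.3 expects that COVID-19 may bring more withdrawals and losses.

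**Working it through.** **Nothing to reproduce.** The documents give no figure for retention, loss or yearly percentages in Years 2 to 5.

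**Inputs**
- Yearly death percentage among subjects of known status: 0.564%, for illustration. This is the mortality rate in protocol Section 8.4.1 (14/2,484).
- Yearly malignancy percentage among those known: 0.53%, for illustration. It is the background rate per 100 patient-years in protocol Section 1.2, and excludes NMSC.
- u, the share of a yearly subset that is lost or withdrawn: **assumption**, 1% to 20%.
- Share of the As-Treated population in the subset: **assumption**, 90%.

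**Formulas.** Let the subset be N = K + U, with K of known status, U lost or withdrawn, u = U/N, and D events observed.
- Planned percentage: D/N = (D/K) × (1 − u).
- Ascertained share of As-Treated: 90% × (1 − u), where Table 1.1 would read 90%.

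| u | Deaths: 0.564% shown as | Malignancy: 0.53% shown as | Ascertained when Table 1.1 reads 90% |
|---|---|---|---|
| 1% | 0.56% | 0.52% | 89.1% |
| 2% | 0.55% | 0.52% | 88.2% |
| 5% | 0.54% | 0.50% | 85.5% |
| 10% | 0.51% | 0.48% | 81.0% |
| 20% | 0.45% | 0.42% | 72.0% |

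Deaths and malignancies are reported to two decimals (Section 5.6), so a change of this kind can appear in print.

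**Unequal loss by arm.** With equal risks of 0.564% and assumed u of 5% and 10%, the table shows 0.536% and 0.508%, a ratio of 0.95/0.90 = 1.06. With 5% and 15% the ratio is 0.95/0.85 = 1.12. Nothing in the documents says that loss differs by arm.

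**Can the known-status denominator be rebuilt?** For malignancy, largely yes: Table 3.9 gives the subjects with and without a new malignancy. For deaths, only in the year in which the Lost or Withdrew form was filed, by subtracting those rows of Table 3.1. In the earlier back-filled years the subject falls under Not completed, together with subjects whom a later form shows Alive or Dead, and the table does not separate them.

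**Subject-year rates.** Tables 3.6–3.8 and 3.14 do not use these denominators.

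**The case against.** The case for leaving the plan alone has five parts.

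1. *Losses are already shown.* Table 3.1 gives them by year and arm, Table 3.9 has its Not completed row, and Listings 1 and 5 give subject-level status. The SOC/PT tables give counts as well as percentages. This stands for Tables 3.1 and 3.9, so a reader who inferred that the plan conceals losses, or counts every unknown outcome as a non-event throughout, would be wrong. It does not answer Tables 1.1–1.4, the SOC/PT tables, or the mixed Not completed row.
2. *The size rests on site behaviour.* If Lost to Follow-up is entered once, in the year of loss, the subset is close to the number at risk at the start of that year, which is a reasonable denominator. This stands; the documents do not say how often the mark is repeated or entered late.
3. *Withdrew Consent is not simply unknown.* Section 5.6.1.1 takes such a subject as alive at the contact date. This stands for vital status to that date, but it does not supply a malignancy answer.
4. *The known-status percentage is not the truth.* It discards part-year observation while keeping every death, and can err upward. This stands. The planned percentage is right if no unknown subject had an event, the known-status percentage if unknown subjects had the same risk, and neither if loss is related to prognosis.
5. *The outputs are descriptive.* Sections 2.4 and 5.5 plan no hypothesis tests, and the rates per subject year handle censoring. This limits the consequence, but those rates are not given by SOC/PT.

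**Conclusion.** The point holds as a matter of definition wherever at least one subject's last survival form is marked Lost to Follow-up or Withdrew Consent. Table 1.1 then overstates ascertainment, Tables 1.2–1.4 describe a mixture, and the yearly SOC/PT percentages contain subjects of unknown status without saying how many.

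The size cannot be taken from the documents. The relative reduction equals u, so it is 1% to 20% over the assumed range, and the overstatement in Table 1.1 is the subset's share of As-Treated times u (9 percentage points at 90% and u = 10%).

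A reader might go further and infer that all Years 2 to 5 mortality and malignancy results are biased downward. The documents do not support that: the cumulative subject-year rates end each subject's time by their own dates. Nor do they support a particular loss share; Section 2.3 gives no number and adds that some missing data may be filled in later. This is a change that should be made for clear reporting; it does not invalidate the follow-up.

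**What to change.** Leave the existing subsets as they are for the person-time rules in Sections 5.6.2.6, 5.6.2.8 and 5.6.2.9. Restricting the last completed visit to Alive or Dead would look simpler but would alter the rates. For example, a subject whose only follow-up form is a Year 2 form marked Lost to Follow-up, last known alive on Day 600, now contributes 600 days. Outside every subset that subject would be cut to 365, losing 235 observed days.

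Instead:

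1. Add a separate status-ascertained flag for each year. For vital status: Alive or Dead at that visit, or shown by a later form. For malignancy: question answered YES or NO.
2. Use the flag for the in-follow-up counts in Table 1.1 and for the populations in Tables 1.2–1.4.
3. In the yearly death and malignancy tables, show by arm the number with unknown status, and give the percentage among those ascertained beside the planned percentage.

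Cost: a RAP amendment, one derived flag per year and endpoint, and extra rows in the shells. Stated retention will look less favourable, and the Year 2 figures already reported need restating once, in the final report.

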4.1. Protocol Deviations

Important protocol deviations relating to the Years 2 to 5 post-treatment follow-up period will be listed. Any protocol deviations due to COVID-19 will be prefixed with 'COVID-19'. Deviations already reported for the Week 52 double-blind treatment period (including deviations related to study inclusion/exclusion criteria) will not be considered, as these are reported separately as part of the Week 52 double-blind treatment period SAC.

Protocol deviations will be tracked by the study team throughout the conduct of the study in accordance with the Protocol Deviation Management Plan (PDMP) for the annual follow-up phase [13 August 2019, Version 1.2]. If the PDMP is updated, the most current version of the PDMP will be used.

- Data will be reviewed on an ongoing basis and prior to freezing the database to ensure all important deviations are captured and categorized on the protocol deviations dataset.
- This dataset will be the basis for the listing of protocol deviations.
- Year 1 PDs which were identified and reported after completion of the Week 52 CSR but before 25 Sep 2019 were described in the Year 2 post-treatment follow-up report. Year 1 PDs which were identified and reported between 26 Sep 2019 and 23 Sep 2020 will be described in the Year 3 post-treatment follow-up report, and similarly for the Year 4 post-treatment follow-up report. All Year 1 PDs which were identified and reported after completion of the Week 52 CSR will be included in the final follow-up report.
- For the Year 3 post-treatment follow-up report, non-important protocol deviations due to COVID-19 will be provided in a PDF file directly from CTMS, for inclusion in an appendix in the Year 3 post-treatment follow-up report. For Year 4 and Year 5 reporting, non-important protocol deviations will be added to the SDTM DV data and a listing of non-important protocol deviations due to COVID-19 will be produced for inclusion in an appendix in the Year 4 and Year 5 post-treatment follow-up reports.

5. CONSIDERATIONS FOR DATA ANALYSES AND DATA HANDLING CONVENTIONS

5.1. Study Treatment & Subgroup Display Descriptors

In the Years 2 to 5 post-treatment follow-up period, subjects no longer receive study treatment, but instead receive physician directed standard of care. The following treatment descriptors from the Week 52 double-blind treatment period will be used on all data tabulations:

- Placebo
- Belimumab 10 mg/kg

In all summary tables, the data will also be presented for all subjects using a Total column.

A footnote will be added to all displays to indicate that subjects in the post-treatment follow-up period are no longer receiving study treatment, and the treatment group assignment is based on treatment received during the Week 52 double-blind treatment period part of the study.

5.2. Baseline Definitions

Demographic and baseline characteristics will be derived as described in the Week 52 double-blind treatment period RAP. Any summaries of demographic and baseline characteristics data presented as part of the Years 2 to 5 post-treatment follow-up period will summarize the demographic or baseline data as at the start of the Week 52 double-blind treatment period.

Analysis age is derived in years relative to the treatment start date for randomized subjects, and is calculated in SAS as follows:

INTCK ('YEAR', Date of birth, Date of treatment start date, 'C').

Region will be presented as US/Canada, Central America/South America/Mexico, Europe/Australia/Israel, and Asia.

Race will be presented in the demography table as Black vs. Other. The Black category is defined as subjects who are in the race category "Black or African American". The race hierarchy rule (Section 5.6.2.1) will not apply and a subject will be categorized as Black if they have selected multiple race categories and any of them is "Black or African American".

SLE Disease Duration is defined as

$$\frac{\text{Treatment Start date} - \text{SLE diagnosis date} + 1}{365.25}$$

If either date is missing, then SLE Disease Duration will be missing. Partial dates for SLE diagnosis date will be imputed as described in Section 5.6.1.1.

Screening SELENA SLEDAI category will be presented as ≤ 9 and ≥ 10 . Note: if any individual item is missing the total score cannot be calculated, however if the subject can be definitively categorized as ≤ 9 or ≥ 10 regardless of the response to the missing item(s) then the appropriate category will be assigned.

Screening Complement Levels and Anti-dsDNA categories (Low Complement and High Anti-dsDNA binding, Not (Low Complement and High Anti-dsDNA binding)) will be derived from the screening SELENA SLEDAI assessment. This is intended to be an indicator of high versus low disease activity. Note: If the evaluations to the SELENA SLEDAI assessment questions “Low Complement” and “Increased DNA Binding” are both missing, the subject will not be classified into one of the categories. If either item is marked “No”, the subject will be classified into the Not (Low Complement and High Anti-dsDNA binding) group regardless of whether the other item is missing or “Yes”.

Complement Levels (Low, Not Low) and Anti-dsDNA Binding (High, Not High) will also be derived from the screening SELENA SLEDAI assessment.

Baseline Systemic Lupus International Collaborating Clinics (SLICC)/American College of Rheumatology (ACR) Damage Index will be derived as specified in Section 9.5.19 and Appendix 5 of the Week 52 double-blind treatment period RAP. Baseline SLICC category will be also be categorized as 0, 1 or >1 .

